8.3 Statistical analysis plan

Initially, descriptive data will characterise the study sample. A descriptive statistical analysis will provide estimates of the extent to which, between phase 1 and phase 3, the use of the MSK-Tracker changed the content and time spent on topics of patient concern in the clinic consultations. A formal hypothesis testing of the effectiveness of the MSK-Tracker to empower patients using the patient

enablement scale will be conducted. Estimates of mean differences will be calculated between phase 1 and phase 3 with 95% confidence intervals (and with adjustment for any important differences between phase 1 and phase 3 participants, if appropriate). Additionally, by calculating between-group effect sizes on a range of clinical outcomes, the analysis will seek to identify on which outcomes the MSK-Tracker implementation has had impact. If a clinically meaningful difference on an outcome lies within the confidence interval, this will support evidence of an effect of the MSK-Tracker. Changes in clinician behaviours reported on the case report forms will be examined to test if there are significant differences in these behaviours between 'before' and 'after' phases i.e. phase 1 and phase 3.

Feasibility will be determined if greater than 50% of both patients and clinicians agree that the MSK-Tracker is acceptable and useful in routine clinical care based on items in the 3 month follow-up questionnaire to patients, and the interviews with patients and clinicians in phase 3.

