The primary outcome of this trial is the patient enablement instrument (PEI)¹ at 2 week follow up. As patients are asked to retrospectively rate the level of enablement, at the 2-week follow up, as a result of their visit to the Staffordshire Musculoskeletal Interface Service we only have a score at a single time point (and not a change score) for each group of patients in Phase 1 and Phase 3. The Patient Enablement Instrument consists of six items graded on three-point scales. It is scored between 0 and 12 and a high score represents more enablement. The sample size was generated based on that required for an independent groups two-sample t-test with a two tailed 5% significance level at 80% power. As no Minimally Clinically Important Difference (MCID) relevant to the specific context could be found for the PEI, the study is powered to find a 0.40 effect size – representative of a small to medium effect.² The expected SD for the population is 3.86¹ (taken from Howie et al. 1998) thus, the implied MCID between the groups would be a score of 1.55 scale points. Accordingly, the required sample is 100 in each arm. If we account for 20% dropout and missingness, the target recruitment is 120 in both phases 1 and 3.

6. Participant characteristics

Baseline characteristics for participants will be displayed in relation to the two groups of participants, i.e., those who are enrolled Phase 1 and those who are enrolled in Phase 3. Given the fact that patient groups are not randomly allocated hypothesis testing will be done comparing the groups at baseline for comparability.

See Tables in section 9 for details of which variables will be collected and how they will be reported.

7. Methods of analysis

Descriptive statistics:

For all outcomes, numerical variables will be summarised as either mean (SD) or median (IQR) depending on the skew of the distribution of the variable in question. Categorical variables will be described as frequencies and percentages.

Primary outcome measure:

A two-tailed independent sample t-test will be conducted to compare the mean PEI score in Phase 1 with that in Phase 3. An effect size, Cohen's Delta, and 95% confidence intervals will be reported for the mean difference between scores. A p-value will be reported with a significance level rate of < 5% leading to a rejection of the null hypothesis of no difference between the two groups.

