Model residuals will be checked for normality, if deviation is found appropriate transformations will be made to the PEI score. Exploration of patterns of missingness will be undertaken to look for potential associates with baseline. Under the assumption of Missing at Random (MAR) missing data on the primary outcome measure will be imputed via the multiple imputation by chained equation (MICE) method³. Sensitivity analysis will be conducted to assess impact of the MAR assumption. Analyses will be done with missing values both ± 1.55 scale points (the implied MCID) on the PEI – to model the potential effect of Missing Not at Random Bias (truncated between 0 – 12).

Secondary outcome measures:

Secondary outcome measures will be analysed via t-test. Effect sizes and 95% confidence intervals will be reported for all measures. P-values will be reported and a <5% rejection criterion will be utilised. No sensitivity analyses will be undertaken and no corrections for multiplicity will be made for the secondary outcomes.

Feasibility outcomes:

Only descriptive statistics for the feasibility outcomes will be reported. These will be counts and percentages with an appropriate denominator for each measure.

Technical details:

It is envisioned that R (current version 3.5.1) will be used for all analyses. The primary outcome will be analysed by the two study statisticians, unblinded. The statistical analyses and associated datasets will be kept in the appropriate section of the trial master file on the internal secure network.

8. References

1. Howie JG, Heaney DJ, Maxwell M, Walker JJ. A comparison of a patient enablement instrument (PEI) against two established satisfaction scales as an outcome measure of

primary care consultations. *Fam Pract.* 1998;15(2):165-171.

2. Cohen J. A Power Primer. *Psychol Bull.* 1992;112(1):155-159.

9. Tables/Figures

Feasibility/process outcomes

Potential participants	Phase 1 (before)	Phase 3 (after)	Total
Number of patients invited to take part			
Actual participants:			
Study consent & Completed baseline survey			
Consultation audio recording			
Clinician completed case report form in clinic			
Patient received clinic summary action plan			
Accessed goal setting module			
Patient completed 2-week FU survey			
Patient needed a reminder email for 2-week FU survey			
Patient completed 3-month FU survey			

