Hours missed from work in last 7 days because of problem- Mean (SD) (only working patients)					
Hours missed from work in last 7 days for other reasons- Mean (SD) (only working patients)					
Hours worked in last 7 days - Mean (SD) (only working patients)					
Joint and muscle symptoms affect your productivity while working - Mean (SD) (only working patients)					
Joint and muscle symptoms affect ability to do regular daily activities, other than work - Mean (SD) (only working patients)					
WPAI Derived Measures:					
Percent work time missed due to problem:					
Percent impairment while working due to problem					
Percent overall work impairment due to problem					
Percent activity impairment due to problem					

Outcome measures at baseline:

Overall MSK Health Status					
MSK-HQ score – Mean (SD) [score range goes from 0 – 56: higher score are milder symptoms] Reference values:					
• Mean MSK-HQ in National FCP pilot = 34 • Mean MSK-HQ in Community physio = 32 • Mean MSK-HQ in GP sample = 30 • Mean MSK-HQ in Ortho hip and knee waiting list sample = 27					
Patient Activation Level					
The Consumer Health Activation Index (CHAI) score – Mean (SD) [score range goes from 0-100: higher score is greater health engagement, understanding, confidence and knowledge] Reference values:					
• In a sample of 10,000 American adults, mean CHAI was 80.					
Low (CHAI score 0-79)					
Moderate (CHAI score 80-94)					
High (CHAI score 95-100)					

Conclusion: There were no differences in patient outcomes between before and after phases

Case Report form completed by clinicians online

	Phase 1 (n=93)	Phase 3 (n=83)	Total
Review Decision			
Review			
ReviewPendingResults			
SOS Appt			
Discharged			
Treatment decision			

Injection Given		
Injection Given Opt (IM)		
Injection Given Opt (SC)		
Injection Given Opt (IA)		
Advice Given		
Treatment Declined		
No Change To Current Treatment		
No Treatment Needed		
Treatment Recommendations To GP		
New Treatment Started		
Amendments To Current Treatment		
Investigations		
Immunology		
Microbiology		
Xray		
MRI		
MRIOpt		
USound		
CTScan		
SynovialFluid		
Isotope		
Echo		
ECG		
PFT		
Haematology		
Biochemistry		
MSSU		
24HrUrine		
Capillaroscopy		
Dexa		
Neurophysiology		
Other		
Referrals		
Physio		
Podiatry		
OT		
Splinting		
Orthotics		
Chronic Pain		
Pain Clinic		
Clinical Diagnoses:		
Shoulder		
Adhesive Capsulitis		
GlenohumeralOA		
ACIOA		
Subacromial Bursitis		
Rotor Cuff Impingement		
Calcific Tendomitis		

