Patient enablement index – Mean (SD) [score range is 0 to 12: higher scores = better empowerment] This items asks – “As a result of your visit to the clinic, do you feel you are:” (options - Much better=2, Better=1, Same=0)					
• Able to understand your illness					
• Able to cope with your illness					
• Able to keep yourself healthy					
• Able to cope with life					
• Confident about your health					
• Able to help yourself					
Reference values: In a GP sample patient mean PEI score was 4 points (1 wk later)					
MSK-HQ score – Mean (SD)					
Reference score at Follow-up:					
• Mean MSK-HQ in National FCP pilot = 41					
• Mean MSK-HQ in Community physio = 42					
• Mean MSK-HQ in GP sample = 37					
• Mean MSK-HQ in Ortho hip and knee post-surgery = 42					
MSK-HQ BL to 2Wk change score – Mean (SD)					
Percentage of patients who achieved MCID (>= 6 points)					
The Consumer Health Activation Index (CHAI) score – Mean (SD) ^a					
There is no reference value yet for this score					
Low (CHAI score 0-79)					
Moderate (CHAI score 80-94)					
High (CHAI score 95-100)					
The Consumer Health Activation Index (CHAI) BL-2W change score – Mean (SD)					
Percentage of patients who moved to an improved CHAI category					
Valuing Patients as Individuals Scale – Care and respect [scores range from 5 to 15: higher is better valued] The item asks if patients felt:					
- The clinic staff listened attentively to what they said					
- The clinic staff were very approachable and easy to talk to					
- The clinic staff treated me kindly					
There are no reference values yet, but this score is high					
Valuing Patients as Individuals – Understanding & engagement [scores range from 5 to 15: higher is better valued] The item asks if patients felt:					
- My problems were regarded as important by the therapist					
- The therapist answered all my questions					
- The therapist treated me as an intelligent human being					
There are no reference values yet, but this score is high					

Patient reported experience measures at 2 weeks

Patient reported experience measures at 2 weeks					
Friends and Family Test:					
How likely are you to recommend this service to friends and family if they need similar care or treatment?					
Extremely likely					
Likely					
Neither likely nor unlikely					
Unlikely					
Extremely unlikely					
Don't know					
Was it easy for you to get to the clinic?					
Very easy					
Easy					
Uncertain					
Not easy					
Not easy at all					

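### SAP table shells contain report-style findings, including a 'no differences' conclusion at baseline that significance tests could not support, and the PEI transformation rule would move the primary result off its own scale

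*SAP*

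**What the plan says.** SAP section 9 (Tables/Figures) is a set of shells for the report. Three items in it are not shell text:

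- After the table headed "Outcome measures at baseline", which holds MSK-HQ and CHAI rows without values, stands "Conclusion: There were no differences in patient outcomes between before and after phases".
- The next table, the clinician case report form (CRF), has its columns headed with n=93 for Phase 1 and n=83 for Phase 3.
- In the 2-week table, "There are no reference values yet, but this score is high" appears under each of the two Valuing Patients as Individuals scores.

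The body of the SAP is in the future tense. Section 6 says that, because patients are not randomly allocated, "hypothesis testing will be done comparing the groups at baseline for comparability". Section 7 fixes the primary analysis: "A two-tailed independent sample t-test will be conducted to compare the mean PEI score in Phase 1 with that in Phase 3", with an effect size and a 95% confidence interval for the mean difference. It then adds that residuals will be checked for normality and "if deviation is found appropriate transformations will be made to the PEI score". Section 7 also states "The primary outcome will be analysed by the two study statisticians, unblinded".

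Protocol section 8.3 plans mean differences between Phases 1 and 3 with 95% confidence intervals, "with adjustment for any important differences between phase 1 and phase 3 participants, if appropriate".

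**The concern.** This is a non-randomised before-and-after comparison with different patients in each phase. How far the phase contrast can be read as an effect of the MSK-Tracker depends on how alike the two groups were at the start. The protocol makes adjustment conditional on that judgement, so a 'no differences' sentence in the plan answers the question before the tables are filled.

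The sentence would also be a weak inference if it came from the planned tests. A non-significant baseline p-value says that the data could not exclude zero. It does not say that the imbalance is too small to bias a comparison designed around 0.40 SD.

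The transformation rule is a second, separate weakness. It leaves the form of the primary outcome to analysts who can see phase membership, names neither trigger nor transformation, and would change the scale of a result whose target is stated in PEI points.

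**Working it through.** **Do the filled counts match a planned number?** The planned numbers per phase are 100 evaluable (both documents), 120 recruited (SAP section 5) and 200 recruited (protocol section 8.1). The counts 93 and 83 equal none of these. They are 78% and 69% of 120, and 47% and 42% of 200. Unequal, unrounded counts read as observed CRF numbers or pasted report text.

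**The plan's own figure.** For a standardised effect of 0.40, two-sided 5% and 80% power, an exact two-sample t-test needs 99.1 per group, that is 100, as stated. The implied difference is 0.40 × 3.86 = 1.544, stated as 1.55 points.

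**What can a non-significant baseline test show?** Patients complete the baseline survey before they give consent (protocol section 7.2), so the recruitment targets are the natural baseline denominators. For a true standardised imbalance *d*:

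- 95% half-width = 1.96 × √(1/n₁ + 1/n₂)
- P(non-significant) = 1 − power of the two-sided 5% t-test, with noncentrality d / √(1/n₁ + 1/n₂)

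At 120 per phase, √(2/120) = 0.129. The half-width is 1.96 × 0.129 = 0.25 SD, and for d = 0.30 the noncentrality is 0.30/0.129 = 2.32.

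| Baseline n per phase | Half-width (SD) | P(non-significant), d = 0.30 | P(non-significant), d = 0.20 |
|---|---|---|---|
| 120 / 120 (SAP target) | ±0.25 | 36% | 66% |
| 200 / 200 (protocol target) | ±0.20 | 15% | 49% |
| 93 / 83 (only if these were also the baseline numbers) | ±0.30 | 49% | 74% |

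An imbalance of 0.30 SD is three quarters of the 0.40 target effect (0.30/0.40 = 0.75), and 0.20 SD is half of it.

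**Would the normality rule be triggered?** Inputs: PEI runs from 0 to 12 (SAP section 5), SD 3.86 (SAP section 5), and mean about 4, the GP reference value in the section 9 shell. Zero is then only 4/3.86 = 1.04 SD below the mean, so a normal curve with these values would put about 15% of its mass below the lowest possible score. In practice that mass piles up at zero.

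The documents do not give the shape of the distribution, so I simulated two that match this mean and SD: a beta-binomial on 0–12, and a rounded normal censored at 0 and 12. With 100 per phase:

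- Residuals failed a Shapiro–Wilk test at 5% in all 2,000 simulated trials under each shape.
- With no true difference, the raw-scale t-test rejected in 5.4% and 4.8% of 10,000 trials respectively, close to the nominal 5%.

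So the rule would almost always fire, although the raw-scale test does not need rescuing.

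**What would the transformation disturb?** Three items in the SAP are defined in raw PEI points: the mean difference with its confidence interval, the implied 1.55-point difference, and the missing-data sensitivity analysis that shifts values by ±1.55 and truncates at 0 and 12. On a square-root or log scale, for example, none of these carries over directly.

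**The case against.** The strongest reply is that the stray lines are leftovers without force. Section 6 requires baseline comparisons and the baseline table has empty confidence-interval and p-value columns, so an analyst following the plan would fill them in whatever the sentence says. The SAP's primary t-test is unadjusted whatever the baseline shows, so the sentence changes no analysis in the SAP itself. This stands. The link to adjustment runs only through protocol section 8.3, and there the prejudgement matters.

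A reader might infer more than the text supports:

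- *That the primary result was known or already settled.* Every result cell is empty, including PEI at both time points. The conclusion follows the baseline table, the counts head a CRF table, and the 'high' comment concerns a secondary experience scale.
- *That the plan was written after the data were seen.* The counts and comments suggest that some data from both phases had been tabulated, or that report text was pasted in. The SAP front matter is not available here, so no date or sign-off can be checked, and its absence cannot be held against the plan.
- *That the choice between mean and median leaves the primary analysis open.* That choice sits under descriptive statistics. The primary contrast is already a difference in means.
- *That 93 and 83 show a shortfall in power.* They are CRF counts. The feasibility table lists CRF completion separately from baseline and 2-week survey completion, and no PEI denominator is given.

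Unblinded analysis is openly declared and is not a fault in itself. It matters here only because it is combined with an unspecified transformation.

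**Conclusion.** The point holds as a correction that should be made, not as evidence that the primary result was fixed. The SAP states findings that a plan should not contain. The main one could not be supported by the tests planned for it: a 0.30 SD imbalance would go undetected 36% of the time at 120 per phase and 15% at 200. The 49% figure applies only if 93 and 83 were also the baseline numbers, which the documents do not show.

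The transformation rule is the one primary-analysis choice in this point that would give a worse result if followed. This conclusion rests on the stated SD, on the GP reference mean of about 4 carrying over to this clinic, and on the two assumed score shapes. A mean nearer the middle of the scale would reduce the skew, but the score would still be bounded and discrete.

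**What to change.** In the SAP:

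1. Delete the conclusion sentence, both comments that the score is high, and the filled CRF counts.
2. Replace the baseline significance tests in section 6, and the p-value column of the baseline table, with standardised differences and 95% confidence intervals. Make these the basis for judging comparability and for deciding on the adjustment in protocol section 8.3.
3. Keep the primary PEI analysis on the raw 0–12 scale as a mean difference with 95% confidence interval. Allow a transformed analysis only as a sensitivity analysis.
4. If data from either phase had been seen when this version was finalised, say which data, by whom and when, and label choices made afterwards as post hoc.

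The cost is SAP wording only; no extra patients or data are needed. The one downside is that some analyses may have to be reported as post hoc.
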